7.3 Sensitivity Analyses

A sensitivity analysis will be conducted for PFS. The calculation of PFS will be the same as described in Section 7.1.1 except that subjects will also be censored at the latest tumor assessment prior to the start of a new anti-cancer therapy.

If any subjects are censored because they missed 2 tumor assessments, a second sensitivity analysis will be conducted to include these subjects as events. Otherwise, the calculation of PFS will be the same as described in Section 7.1.1.

A third sensitivity analysis will include subjects in Part 1 cohorts and be summarized by integrated treatment group.

The same statistical analysis methods used for the primary analysis of PFS, ie, log-rank test and Cox regression, will be used for all of these sensitivity analyses.

The best % change from baseline in target tumor diameters will be presented for each subject in a waterfall plot by study cohort.

8. SAFETY EVALUATION

8.1 Analysis of Primary Safety Outcome Measure

For the determination of the RP2D, the analysis of the occurrence of DLTs will be performed on a subset of the safety analysis set, including all evaluable subjects. Subjects will be considered evaluable once they either complete their first treatment cycle or withdraw from study during the first treatment cycle due to DLT. The RP2D will be defined as the highest dose level examined at which < 33% of evaluable subjects experience a DLT during the first treatment cycle.

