8.2.1.1 Stopping Criteria for Dose Escalation

For each combination, enrollment will proceed according to the following rules based on the occurrence of DLTs:

- If zero out of 3 evaluable subjects experience a DLT during the first 28 days after the first administration of study drug at the first dose level, the second dose level will be opened for enrollment after review of the safety data by the DRC
- If 1 out of 3 evaluable subjects experiences a DLT during the first 28 days after administration of study drug at the first dose level, 3 additional subjects will be enrolled at the first dose level, for a total of 6 evaluable subjects. After review of the safety data of all 6 evaluable subjects, the DRC will decide if the second dose level or a lower dose level will be explored
- If 2 or more evaluable subjects experience a DLT during the first 28 days after the first administration of study drug at the first dose level, the second dose level will not be open to enrollment, and the DRC will decide if a lower dose level will be explored

See Section 8.2.3 for DLT definition. See [Figure 1](#) for a schematic of the dose escalation.

Figure 1
Protocol 391401 Dose Escalation Scheme

Abbreviation: DLT=dose-limiting toxicity.

^a A subject is considered evaluable if he/she can be evaluated for adverse events during the first 28 days after first study drug administration, or is withdrawn from the study due to a DLT.

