9.3 Withdrawal and Discontinuation

Any subject may voluntarily withdraw (ie, reduce the degree of participation in the study) consent for continued participation and data collection. The reason for withdrawal will be recorded on the End of Study CRF. Assessments to be performed at the termination visit (including in cases of withdraw or discontinuation) are described in Section 10.3.3.8 and Section 20.2.

Discontinuation (ie, complete withdrawal from study participation) may be due to dropout (ie, active discontinuation by subject) or loss to follow-up (ie, discontinuation by subject without notice or action). Additionally, the investigator and sponsor have the discretion to discontinue any subject from the study if, in their judgment, continued participation would pose an unacceptable risk for the subject.

Subjects also will be withdrawn from treatment or discontinued from further study participation for the following reasons:

- Disease progression according to RECIST v1.1
- Clinical progression due to the subject's underlying malignancy
- Excessive toxicity
- Intercurrent illness unrelated to the subject's underlying malignancy that prevents further participation
- The subject becomes pregnant. IP exposure will be discontinued. Attempts will be made to follow the subject through completion of the pregnancy and up to 1 year post-delivery, if feasible. The investigator will record a narrative description of the course of the pregnancy and its outcome.
- The subject begins lactating. IP exposure will be discontinued. The investigator will record a narrative description of the course of the baby's development.
- Participation in another clinical study involving an investigational product during the course of the study.
- Protocol non-compliance
- Subject withdrawal of consent
- Study closure or termination by the sponsor
- Use of prohibited therapies (see protocol Section 10.4)

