13.4.3 Primary Outcome Measure

13.4.3.1 Primary Safety Outcome Measure

The primary safety outcome measure is the occurrence of DLTs (Part 1) (see Section 8.4.1).

Where appropriate, point estimates and 95% two-sided confidence intervals (CIs) will be calculated for all safety outcome measures by treatment group.

For the determination of the RP2D, the analysis of the occurrence of DLTs will be performed on a subset of the safety analysis set, including all evaluable subjects. Subjects will be considered evaluable once they either complete their first treatment cycle or withdraw from study during the first treatment cycle due to DLT. The percentage of subjects experiencing DLT during their first treatment cycle will be displayed along with corresponding 95% CIs, where appropriate. The RP2D will be defined as the highest dose level examined at which <33% of evaluable subjects experience a DLT during the first treatment cycle.

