15.4 Safety Monitoring

15.4.1 Data Safety Monitoring (Part 1)

A Data Review Committee (DRC) will review accumulating unblinded safety data of the subjects enrolled in Part 1.

The DRC members must include at least one participating investigator, the sponsor-designated Medical Monitor, and a sponsor representative (non-voting).

The DRC will meet for safety reviews after 3 subjects in a dosing cohort have completed the first treatment cycle (ie, after 28 days) to decide if additional subjects must be enrolled or if the next dose level can be opened. All available safety data will also be provided for subjects who discontinue prior to this time. At the end of the escalation phase, the DRC will determine the RP2D for each imalumab combination, or decide if an intermediate dose level will be explored.

Decisions will be made using the stopping rules and dose escalation procedures defined within the protocol (see Section 8.2.1.1) and shown in [Figure 1](#).

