- ^k A tumor measurement should be obtained at the End of Study/Early Termination visit, if no disease progression was confirmed previously and this visit occurs $>$ 4 weeks after the last scan; no additional scans will be required if disease progression is confirmed at this visit. A tumor measurement should be obtained at the Safety Follow-up visit, if no disease progression was confirmed previously and this visit occurs $>$ 4 weeks after the last scan.
- ^l For subjects receiving imalumab treatment, blood samples for PK (imalumab plasma levels) and PD biomarkers (oxMIF and total MIF) will be collected at the times indicated in **Table 6. Cycle 1 only:** Blood samples will be collected predose and postdose on Day 1, on either Day 2 (24 \pm 4 h post first dose) OR Day 4 (72 \pm 8 h post first dose), and then predose and postdose on Day 8, Day 15, and Day 22.
- Subsequent treatment cycles:*** Blood samples will be collected predose and postdose only on Day 1.
- ^m Optional exploratory analysis for subjects treated with imalumab in combination with 5-FU/LV or panitumumab.
- ⁿ AEs to be collected on a continuous basis until the Safety Follow-up Visit.

In subjects randomized to SoC (Part 2, Arm B), all Screening assessments and procedures should be performed according to [Table 4](#) and Section 10.3.1. All Baseline assessments and procedures should be performed at C1D1 predose according to [Table 4](#) and Section 10.3.2. These assessments should be completed prior to drug administration. If the study subject is receiving SoC on a 4-week treatment cycle, the schedule of assessments should be as follows:

Table 4 Schedule of Study Procedures and Assessments: SoC Following Randomization (4-Week Cycles or if Subject is on Best Supportive Care)								
Trial Periods	Screening Visit	Baseline Visit	Study Visits Per Treatment Cycle ^a				End of Study/ Early Termination Visit	Safety Follow-Up Visit ^b
Study Days	Days -28 to -1	Day 1 Predose	Days 1 to 7	Days 8 to 14	Days 15 to 21	Days 22 to 28		
Treatment Schedule								
SoC (Part 2, Arm B)			Dose according to Product Label					
Visit window (days)		±2	±2	±2	±2	±2	±2	±7
Informed consent ^c	X							
Eligibility criteria	X	X						
Demographics	X							
Relevant medical and surgical history	X							
Entry into IRT System	X	X ^d					X	
Vital signs ^e	X	X	Day 1	Day 8	Day 15	Day 22	X	X
Physical examination	X	X	Day 1		Day 15		X	X
ECOG PS	X	X	Day 1				X	X

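### SAP 8.1's definition of DLT-evaluable can drop a DLT from the primary safety result when the subject leaves before Day 28 for another reason

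*SAP*

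**What the plan says.** DLT occurrence in Part 1 is the primary safety outcome (Protocol 8.4.1, SAP 3.2.1). The documents define the evaluable subjects in two ways.

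- **Analysis definition.** SAP 8.1 takes subjects to be "evaluable once they either complete their first treatment cycle or withdraw from study during the first treatment cycle due to DLT". Protocol 13.4.3.1 has the same definition ("Subjects will be considered evaluable once they either complete their first treatment cycle", or withdraw because of a DLT). Both then define the RP2D as the highest dose studied with a DLT rate below 33% in that set.
- **Escalation definition.** Footnote a to Figure 1 in Protocol 8.2.1.1 says: "A subject is considered evaluable if he/she can be evaluated for adverse events during the first 28 days after first study drug administration". It also admits subjects withdrawn because of a DLT.

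The DRC works from the second. Protocol 15.4.1 states "Decisions will be made using the stopping rules and dose escalation procedures defined within the protocol", pointing to 8.2.1.1, and adds "All available safety data will also be provided for subjects who discontinue prior to this time".

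Subjects can leave in cycle 1 for reasons other than a DLT. Protocol 9.3 says "Subjects also will be withdrawn from treatment or discontinued from further study participation for the following reasons", and its list includes clinical progression and intercurrent illness. Adverse events are still sought after treatment stops: note n to Protocol Table 3 reads "AEs to be collected on a continuous basis until the Safety Follow-up Visit", and note b puts that visit 30 (±7) days after the last dose.

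**The concern.** The analysis definition makes inclusion depend on why a subject left. A DLT followed by departure because of that DLT is counted. The same DLT followed by departure for progression is not, although the toxicity was seen inside the 28-day window. The rule can therefore remove an observed event from the primary safety numerator, and the error runs in the dose-favouring direction.

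What is at stake is the DLT rate reported in support of the dose, and whether it agrees with the n/N on which the DRC acted. With cohorts this small, a single subject can settle whether the <33% rule is met.

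**Working it through.** **1. Part 1 size, reproduced.** Two combinations × 2 dose levels × 3 to 6 subjects gives 2×2×3 = 12 and 2×2×6 = 24. This matches the stated 12 to 24.

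**2. Who falls in which set.** Completion is read here as 28 days elapsed, following the gloss in Protocol 8.2.1 and 15.4.1.

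| Part 1 subject | Protocol 8.2.1.1, footnote a | SAP 8.1 |
|---|---|---|
| Completes cycle 1, with or without a DLT | in | in |
| Leaves in cycle 1 because of a DLT | in | in |
| Has a DLT, leaves before Day 28 for another reason, AEs assessed to Day 28 | in, DLT counted | **out, DLT lost** |
| No DLT, leaves before Day 28 for another reason, AEs assessed to Day 28 | in | out |
| Leaves before Day 28 for another reason, AE follow-up ends | out | out |

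The third row is the defect. If completion instead means receiving the cycle's doses, a subject whose drug is stopped after a DLT but who stays on study is lost as well.

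**3. What one exclusion does.** Take six treated subjects with two DLTs, one of them in a third-row subject (exact Clopper-Pearson 95% CIs):

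- DLT counted: 2/6 = 33.3% (4.3 to 77.7), not below 33%.
- SAP 8.1 set: 1/5 = 20.0% (0.5 to 71.6), below 33%.
- SAP 8.1 set, subject replaced by one without a DLT: 1/6 = 16.7% (0.4 to 64.1), below 33%.

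**4. How often, under assumptions.** The documents give neither an early-exit rate nor a DLT rate. Assume that a fraction e leaves in the first 28 days for a non-DLT reason, that a fraction p has a DLT, and that the two are independent. Take e = 5%, 10% or 14%, and p = 20% or 30%. The 14% treats the planned 4.25-month median PFS as exponential: 1 − exp(−ln 2 × (28/30.4375)/4.25) = 0.139. That is a high value, because the first on-treatment scan is at Day 56.

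- At least one DLT left out among 12 subjects: 1 − (1 − pe)^12.
- Cohort of 6 moving from not met to met: the multinomial over (DLT or none) × (leaves or stays), summing outcomes where DLTs/6 ≥ 0.33 but the ratio among those who stay is < 0.33.

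| | e = 5% | e = 10% | e = 14% |
|---|---|---|---|
| DLT left out of 12, p = 20% | 11% | 22% | 29% |
| DLT left out of 12, p = 30% | 17% | 31% | 40% |
| Cohort of 6 changes, p = 20% | 2.4% | 4.6% | 6.1% |
| Cohort of 6 changes, p = 30% | 3.2% | 6.2% | 8.3% |

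Read these as upper bounds at the assumed rates. They take every early leaver to be AE-evaluable to Day 28, and they fall if some are not. They also fall when a DLT is itself the usual reason for leaving. The reverse change, from met to not met, has probability at most 0.7% in a cohort of 6.

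**The case against.** **The sets nearly coincide.** Once completion means 28 days elapsed, both definitions largely come down to 28 days observed or withdrawal for a DLT. Protocol 12.1.2 also collects treatment-emergent events only to study discontinuation or 30 days after the last dose, so some early leavers are not evaluable under 8.2.1.1 either, and non-evaluable subjects are replaced. This stands, and it narrows the gap. It does not close it: a DLT seen before an unrelated departure is still excluded by SAP 8.1.

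**The SAP follows the protocol.** A reader might infer that SAP 8.1 departs from the protocol's analysis section. It does not. It repeats 13.4.3.1, so the conflict lies within the protocol and the SAP carries it forward unresolved.

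**Missing output.** A reader might also infer that no DLT output is planned. SAP 8.1 omits the protocol's sentence "The percentage of subjects experiencing DLT during their first treatment cycle will be displayed along with corresponding 95% CIs, where appropriate", and SAP Table 3 has no DLT row. But SAP 5 already sets n and percentages as the default for categorical data. Only the CI is missing, and the protocol itself qualifies it.

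**Conflicting verdicts.** It is tempting to say that the DRC and the SAP would reach opposite verdicts at 1/3 against 0/2. The documents do not support that. The <33% rule is stated only with the 13.4.3.1 and SAP 8.1 set, while 8.2.1.1 works by counts, and 1 of 3 at the first dose level triggers expansion to 6, not a final verdict. For that reason no cohort-of-3 probabilities are given here.

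**Little would be hidden.** Grade 3 or higher and treatment-related events are tabulated by cohort on the whole safety set, and all AEs are listed. The event would appear in the report, but not in the DLT rate.

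**Conclusion.** The definition is wrong as written, and the consequence is limited. It can omit an observed DLT from the primary safety rate, and one omission can turn 33.3% into 20% or 16.7% against a <33% rule. The finding rests on the text of the two definitions and holds even when completion is read as 28 days elapsed. The percentages in step 4 of the working show only scale, because their inputs are assumed.

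A reader might infer that a DLT was in fact missed or that the dose is unsafe. Nothing in the documents shows either. The DRC has all available safety data, including for early discontinuers, and SAP 5.4 already records 10 mg/kg as selected. The effect is confined to the reported Part 1 DLT result and its agreement with the DRC's count. This is a low-priority correction, but a cheap one.

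**What to change.** In SAP 8.1, replace the sentence defining evaluable subjects with:

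> The DLT-evaluable set is all treated Part 1 subjects who (a) had a DLT in the first 28 days, whatever the reason for leaving, or (b) completed the first 28-day cycle without a DLT.

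Add a row to SAP 5.5 recording this against Protocol 8.2.1.1 and 13.4.3.1. Footnote the DLT result for any cohort where the DRC's n/N differed.

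While the section is open, restore the percentage with an exact 95% CI for each of the four Part 1 cohorts. That is an editorial addition, not the repair of a separate defect.

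There is one small downside. Early leavers without a DLT stay excluded, so N can still differ from the DRC's. Three completers with one DLT plus one such leaver give 1/3 here and 1/4 under 8.2.1.1 if the leaver is AE-evaluable. The footnote is there to make that visible.

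The cost is one sentence, one row in SAP 5.5, and a short table for 12 to 24 subjects whose safety data the DRC reviews in any case. No subjects, visits or new data are needed.

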8.2 Extent of Exposure

The following variables will be calculated:

- Exposure duration (days): date of last dose – date of first dose (C1D1) + 7, 7 is added to exposure duration to account for the 7-day rest period between imalumab administrations.
- Number of cycles: Total number of complete or partial treatment cycles the subject received.
- Number of Subjects with dose interrupted/ dose reduction

For imalumab, the following parameters will be calculated:

- Cumulative dose (mg): Total actual dose (mg) the subject received across all cycles, defined as the sum of actual dose (mg) received across all cycles.
- Calculated cumulative dose level (mg/kg): Cumulative dose (mg) divided by the average weight (kg) across all cycles.
- Dose intensity (mg/kg/week): {Calculated cumulative dose level (mg/kg) / (exposure duration (days))} x 7
- Expected dose intensity (mg/ kg/week): 7.5 or 10 mg/kg/week based on treatment arm
- Relative dose intensity (%): ((Dose intensity) / (expected dose intensity)) × 100.

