8.7.2 Preparation and Storage of Pooled Product

8.7.2.1 Imalumab

Imalumab solution for injection must be prepared on the day of administration. The initial dose (in mg) will be prepared based on the subject's body weight at screening/baseline. Dose (in mg) will be adjusted when a $\geq 10\%$ change in the subject's weight is observed (compared to the body weight currently being used for the basis of dose preparation).

Volume (ml) = [Dose (mg/kg)/Concentration (mg/mL)] x Subject Weight (kg)

Concentration (mg/mL) = 50 mg/mL

Depending on the amount of imalumab to be administered, the content of multiple vials of imalumab may be pooled into a syringe of appropriate size (maximum of 50 mL), and may require more than one syringe to be filled with imalumab.

The vials will be brought to room temperature. The flip cap is then removed from the study drug vial, and the exposed stopper wiped with alcohol. All imalumab preparations for IV injection must be prepared aseptically under a laminar flow hood and should be inspected visually for particulate matter and discoloration. Only clear or slightly opalescent, colorless to yellow to pink solutions without visible particles are to be administered. No dilution of imalumab is permitted. Further details regarding the preparation of imalumab are provided in the Pharmacy Manual.

Once prepared, the imalumab solution for injection will be kept at room temperature or, if not used immediately, at 2° to 8°C (36° to 46°F). For the latter, the imalumab solution must be allowed sufficient time to equilibrate to room temperature prior to administration, noting that infusion of imalumab shall begin within 7 hours (4 hours prior to aspiration and 3 hours after aspiration) from when the vials are removed from storage. Vials removed from storage to equilibrate to room temperature must not be removed from secondary packaging (original outer box), in order to protect product from light until administration.

Administration of imalumab should be performed in accordance with Section 8.7.3.1.

Do not dilute the imalumab solution with any other solutions or IV fluids unless agreed upon by the sponsor.

8.7.2.2 5-Fluorouracil, Leucovorin, and Panitumumab

Fluorouracil, LV, and panitumumab will be reconstituted according to the package label provided by the manufacturers and according to local pharmaceutical regulations.

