12.1.2 Assessment of Adverse Events

For the purposes of this study, each non-serious untoward medical occurrence experienced by a subject undergoing study-related procedure(s) before first exposure to IP will be recorded on the AE CRF; however, these events will not be considered as AEs and will not be included in the analysis of AEs.

Each TEAE (non-serious AE or SAE) from the first IP exposure until study completion/discontinuation or 30 days (± 7 days) following the last IP treatment will be described on the AE CRF using the medical diagnosis (preferred), or, if no diagnosis could be established at the time of reporting the AE, a symptom or sign, in standard medical terminology in order to avoid the use of vague, ambiguous, or colloquial expressions (see definition in Section 12.1). Each AE will be evaluated by the investigator for:

- Seriousness as defined in Section 12.1.1.1
- Severity as defined in Section 12.1.2.1
- Causal relationship to IP exposure or study procedure as defined in Section 12.1.2.2.

For each AE, the outcome (ie, recovering/resolving, recovered/resolved, recovered/resolved with sequelae, not recovered/not resolved, fatal, unknown) and if applicable action taken (ie, dose increased, dose not changed, dose reduced, drug interrupted, drug withdrawn, not applicable, or unknown) will also be recorded on the AE CRF. Recovering/resolving AEs will be followed until resolution, medically stabilized, or 30 days after the last IP administration, whichever comes first. If the severity rating for an ongoing AE changes before the event resolves, the original AE report will be revised (ie, the event will not be reported as separate AE). During the course of any AE, the highest severity rating will be reported.

Deviations from the protocol-specified dosage (including overdosing [any dose that is at least 20% higher than the highest explored dose level], underdosing [any dose that is lower than the intended explored dose level by 10%], abuse, and withdrawal [see

Section 9.3]), treatment errors (including incorrect route of administration, use of an incorrect product, and deviations from the protocol-defined dosing schedule), failures of expected pharmacological actions, and unexpected therapeutic or clinical benefits will be followed with regard to occurrence of AEs, lack of efficacy, and/or other observations because these events may be reportable to regulatory authorities.

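### Imalumab relative dose intensity uses average on-study weight although doses are set on a held dosing weight, so weight change alone moves it off 100%; the 7-day exposure add-on fits only weekly dosing

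*SAP*

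**What the plan says.** **Dosing rule.** Protocol 8.7.2.1 states: "The initial dose (in mg) will be prepared based on the subject's body weight at screening/baseline". The milligram dose is then adjusted only at a weight change of at least 10%, "compared to the body weight currently being used for the basis of dose preparation". Between such changes the milligram dose stays fixed.

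**Exposure measure.** In SAP 8.2 the numerator is total milligrams, "defined as the sum of actual dose (mg) received across all cycles". It is converted to mg/kg as follows: "Calculated cumulative dose level (mg/kg): Cumulative dose (mg) divided by the average weight (kg) across all cycles". Dose intensity is that figure divided by exposure duration in days, times 7. The reference is "7.5 or 10 mg/kg/week based on treatment arm", and the reported ratio is "Relative dose intensity (%): ((Dose intensity) / (expected dose intensity)) × 100".

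**Exposure duration.** This is last dose date minus first dose date plus 7 days, with the reason "7 is added to exposure duration to account for the 7-day rest period between imalumab administrations". The line stands in a general list that precedes the imalumab-specific parameters. The SAP gives no other rule for the partner drugs, which are given every 2 weeks (Protocol 8.7.4), or for standard of care in 3- or 4-week cycles (Protocol Table 4, footnote a).

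**The concern.** The numerator of the ratio follows one weight and the denominator another. The milligrams given reflect the dosing weight in force; the conversion to mg/kg uses the mean of the weights observed on study. The expected intensity assumes that the two agree. When weight drifts by less than 10%, they do not, and the ratio then reflects weight change as well as delivery.

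This matters because Protocol 10.3.3.1 plans no imalumab dose modification. A reader will take a value below 100% to mean missed, delayed or incomplete doses, and a value near 100% to mean full delivery. One missed dose in 12 to 18 is worth 8.3% to 5.6%, which is the same order as the weight effect. Weight change is also foreseen: SAP 8.6 counts a change of 7% or more as potentially clinically significant, and a 7% change does not trigger re-basing.

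The 7-day add-on raises a smaller question: which drugs the general duration variable is meant to cover.

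**Working it through.** **Inputs.** The formulas are those of SAP 8.2 and the dosing rule is that of Protocol 8.7.2.1. Weight is collected at each visit (Protocol 12.8). Assumptions: a starting weight of 70 kg, which cancels out, and a weight at every weekly dose. For scale, 18 weekly doses are used, since the assumed experimental median PFS of 4.25 months is 4.25 × 52/12 = 18.4 weeks.

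**1. The SAP's reference value, constant weight.** At 10 mg/kg:
- total dose: 18 × 700 mg = 12,600 mg
- dose level: 12,600/70 = 180 mg/kg
- duration: 17 × 7 + 7 = 126 days
- intensity: 180/126 × 7 = 10 mg/kg/week, so RDI is 100%

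The same steps at 7.5 mg/kg give 7.5 mg/kg/week. The formula is right when weight is stable.

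**2. All doses given, weight changing by less than 10%.** RDI = 100 × dosing weight / mean on-study weight.
- Linear 9% loss: mean weight is 0.955 of dosing weight; 100/0.955 = 104.7%.
- Linear 9% gain: 100/1.045 = 95.7%.
- 9% loss immediately after dose 1: mean is (1 + 17 × 0.91)/18 = 0.915; RDI 109.3%.
- 9% gain immediately after dose 1: mean is (1 + 17 × 1.09)/18 = 1.085; RDI 92.2%.

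**3. Limits.** Re-basing keeps current weight between 0.90 and 1.10 of the dosing weight. With full dosing, RDI therefore lies between 100/1.10 = 90.9% and 100/0.90 = 111.1%. Larger linear losses do not widen this: a 15% to 20% loss with re-basing gives 104.2% to 104.6% (12 or 18 doses).

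**4. With missed doses** (missed before the last dose given):

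| Missed | Share of planned dose given | RDI, linear 9% loss | RDI, early 9% loss |
|---|---|---|---|
| 1 of 18 | 94.4% | 98.9% | 103.2% |
| 2 of 18 | 88.9% | 93.1% | 97.1% |
| 1 of 12 | 91.7% | 96.0% | 99.9% |
| 1 of 8 | 87.5% | 91.6% | 95.0% |

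If a share m of planned milligrams is missed, RDI returns to 100% only when mean weight is (1 − m) of the dosing weight. Mean loss stays under 10%, so full masking needs m under 10%. In the other direction, one missed of 18 with a linear 9% gain gives 94.4 × 0.957 = 90.4%, which exaggerates the gap.

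**5. Final dose missed.** Duration ends 7 days after the last dose given. If dose 12 of 12 is missed at constant weight, 11 doses over 77 days give RDI 100%, so that dose is never counted.

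**6. Exposure duration.** For n doses at an interval of d days, the SAP rule gives (n − 1)d + 7, while n doses cover nd days. The shortfall is d − 7: 0 days for weekly dosing, 7 for 2-weekly, 14 for 3-weekly and 21 for 4-weekly. Three 3-weekly doses give 2 × 21 + 7 = 49 against 63 days (22% short). Eight give 154 against 168 (8% short).

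**The case against.** The best defense is that milligrams per kilogram of current weight is a legitimate quantity: a subject whose weight falls while the milligram dose stays fixed does receive more per kilogram. No passage says that relative dose intensity must measure adherence. This stands for the mg/kg/week figure. It does not rescue the ratio, because the expected intensity in its denominator is not what the protocol's dosing rule produces once weight moves.

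The same section also plans total milligrams, number of cycles and the number of subjects with interrupted or reduced doses. A reader might infer that missed doses simply disappear. They do not: a missed share of 10% or more is understated but still shows, and interruptions are counted separately.

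A reader might also infer that the ratio will generally overstate delivery because this population loses weight. The documents give no on-study weight data, and the error runs both ways.

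Finally, the underdosing limit in Protocol 12.1.2 might be taken as a tolerance for this ratio. It concerns a single dose and sets none for a cumulative measure.

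On duration, the SAP ties the 7 days to imalumab by its stated reason, and dose intensity is defined for imalumab only. A reader might infer that control exposure will be understated in a comparison with Arm A, but no such comparison is specified. What stands is that the variable's scope is left open.

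**Conclusion.** The mismatch of weight bases is real and small. With every dose given, relative dose intensity departs from 100% by about 4 to 5 percentage points for a linear 9% weight change, and by at most about +11 or −9 points. It can fully mask or mimic only a missed-dose share under 10%.

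The sizes rest on the assumed weight paths and on averaging weekly weights. The SAP does not say whether the mean uses every visit or one weight per cycle, and the choice matters. For 16 doses with an early 9% loss, weekly weights give 16/(1 + 15 × 0.91) = 109.2%, while four cycle-start weights give 4/(1 + 3 × 0.91) = 107.2%.

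The 7-day rule is exact for imalumab and wrong only if the duration variable is reported for regimens with longer intervals. Both points concern descriptive exposure measures. Neither touches the PFS test, the sample size, the DLT analysis or the RP2D, so this is a minor improvement.

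**What to change.** In SAP 8.2, define imalumab relative dose intensity as 100 × (sum of milligrams given) / (sum of milligrams planned). Each planned dose is the assigned dose level times the dosing weight in force under Protocol 8.7.2.1. Count planned doses over the weekly doses scheduled from C1D1 to treatment discontinuation, so that a dose missed at the end also counts. Weight drift then drops out: 17 of 18 doses at an unchanged dosing weight gives 94.4% whatever the weight path in between. If mg/kg/week at current weight is also of interest, report it separately and state which weights are averaged.

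For exposure duration, either restrict the variable to imalumab or add each regimen's own dosing interval.

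The cost is SAP wording and a short derivation; dosing itself does not change. Protocol 10.3.3.1 already collects planned dose and actual volume per administration, and the concentration is 50 mg/mL. It does not say whether planned dose is recorded in mg or mg/kg. If in mg/kg, the planned milligrams can be rebuilt from the visit weights and the 10% rule.
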